10.4 DESCRIPTION OF STATISTICAL METHODS

10.4.1 GENERAL APPROACH

All summary tables for quantitative parameters will display mean, standard deviation, median, range (minimum and maximum), percentages as well as number of missing data (if relevant). All summary tables for qualitative parameters will display counts, percentages and number of missing data if relevant. Baseline data are defined as the last measurement performed before the first treatment on Visit 2.

All statistical tests will be two-sided. The level of statistical significance for effectiveness analyses is 5% ($\alpha = 0.05$) for all tests of differences. Where appropriate, Paired t-test and/or Wilcoxon Signed-Ranks Test for Matched Pairs will be used to compare the evaluations at the baseline and post treatment sessions. This test will enable us to accept or reject the null hypotheses. Rejection of null hypotheses will establish that:

- The two-sided 95% confidence interval for the difference between the means excludes zero.
- The two means are statistically significantly different at the 5% level ($P < 0.05$) two-sided.

Upon rejection of null hypotheses, further statistical test tools such as Confidence Interval and/or t-test will be used to determine the performance of Venus Viva™ fractional RF System in the treatment of surgical scars following breast augmentation, abdominoplasty or face lift.

In order to accommodate imbalances of some baseline General Aesthetic Improvement Scale (GAIS) and Manchester Scar Scale (MSS) scores, covariate adjustment analysis may be performed in SAP to estimate adjusted treatment effects for the primary endpoint analysis.

The assumption for the statistical test is that the paired differences of baseline and post treatment data are normally distributed.

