7.3.2 ENROLLMENT/BASELINE

Enrollment/Baseline Visit (Visit 2, Day 0)

Once a subject has been confirmed that they continue to meet inclusion/exclusion criteria, they will receive a unique identifying number that will be composed of a two-digit site number and a two-digit subject number in sequence. This unique identifier will be used throughout the entire study and will be entered in the subject's case report form (CRF). The investigator will confirm that the subject still meets the inclusion/exclusion criteria. Vital signs and demographics will be collected and a physical exam will be performed. The subject will complete the POSAS.

Photography

Photographs will be taken prior to first treatment and throughout the study according to specified time points detailed in the Schedule of Events Table (section 7.3.7), utilizing standard scientific equipment. Two sets of photographs will be required, one set for the treated side of the body/face and a second set for the untreated side of the body/face.

The photos should be taken in a private room or area of the clinic under controlled conditions, including the distance, angle, background and lighting in order to achieve high-quality sets of photographs. Direct illumination will not be used. The subject should be placed in the same position each time. As each photograph is taken, it should be viewed to ensure that it is in focus and is similar to its baseline counterpart in all technical aspects, including lighting, distance and angle.

For consistency purposes, the same person should ideally take all study photographs, especially per subject. The digital files should follow a consistent standard naming scheme.

Treatment

Subjects will receive treatment as described in section 7.3.1. Only one side of the body/face will be treated. The same side will be treated for the duration of the study. Only half of a scar will be treated

and remaining half will serve as the control. Following treatment, the investigator will examine the treated area and report immediate and short term response. Subjects will complete the 10 cm discomfort/pain VAS immediately after treatment. A new disposal tip will be used for each patient treatment.

Treatment procedure should include positioning of the patient in a manner that enables comfortable access to the treated anatomical site.

Assessment

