10.4.2 ANALYSIS OF THE PRIMARY PERFORMANCE ENDPOINT(S)

The following will be considered for the analysis primary performance endpoint:

Summary table for differences of baseline, 3-month and 10-month post treatment General Aesthetic Improvement Scale (GAIS) and Manchester Scar Scale (MSS) scores will be displayed as mean difference, standard deviation and standard error. The General Aesthetic Improvement Scale (GAIS) scores is a 5-point scale improvement assessment chart while Manchester Scar Scale (MSS) is two scales whose scores are combined - an overall VAS and seven scar parameters.

Bar, pie charts or graphs indicating scores will also be used to analyse performance, where applicable.

All statistical tests will be two-sided. The level of statistical significance for effectiveness analyses is 5% ($\alpha = 0.05$) for all tests of differences. Where appropriate, Paired t-test and/or Wilcoxon Signed-Ranks Test for Matched Pairs will be used to compare the evaluations of General Aesthetic Improvement Scale (GAIS) scores and Manchester Scar Scale (MSS) scores at 3 and 10 months against baseline. Analysis of Covariance (ANCOVA) may also be used where appropriate.

The Paired t-test and/or Wilcoxon Signed-Ranks Test for Matched Pairs will enable us to accept or reject the null hypotheses. Rejection of null hypotheses will establish that:

- The two-sided 95% confidence interval for the difference between the means excludes zero.
- The two means are statistically significantly different at the 5% level ($P < 0.05$) two-sided.

Upon rejection of null hypotheses, further statistical test tools such as Confidence Interval and/or t-test will be used to test expected primary performance endpoint; that is alternative hypothesis that $H_a \geq 1$. This will be used to determine if the study meets the primary performance endpoint.

General Aesthetic Improvement Scale (GAIS) scores and Manchester Scar Scale (MSS) scores of all subjects who received at least one treatment of Venus Viva™ system for the treatment of surgical scars following breast augmentation, abdominoplasty or face lift and for whom at least one valid post-baseline GAIS and MSS assessment were obtained will be analysed for the primary endpoint. Multiple imputation method or modelling of available data may be used for missing data as appropriate.

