10.5 SAMPLE SIZE

One of the primary performance endpoints outcome measures was used to calculate the study sample size.

Sample size calculation using the subject's improvement of surgical scars at 3 months post-treatment as evaluated by independent blinded reviewer using the General Aesthetic Improvement Scale (GAIS);

- Null and alternate hypotheses:
 - **Null Hypothesis ($H_0: \mu_d = \mu_{post} - \mu_{pre} = 0$)** – There is no improvement of surgical scars at 3 months post-treatment review compared to baseline.
 - **Alternative Hypothesis ($H_a: \mu_d = \mu_{post} - \mu_{pre} \neq 0$)** – There is improvement of surgical scars at 3 months post-treatment review compared to baseline. The improvement of surgical scars will be defined by General Aesthetic Improvement Scale (GAIS) scores evaluated by independent blinded reviewer. Expected mean improvement difference is not less than one (1) GAIS score higher than baseline.
- In view of the nature of this study in regard to treatment period of 3 months and up to 10 months follow-up, we make provision for 30% study drop out, withdrawal or loss to follow-up.
- Due to the natures of 3 types of surgical scars that will be treated in this clinical study, the study will be viewed as 3 groups of cohort studies;
 - breast augmentation cohort group
 - abdominoplasty cohort group
 - face lift cohort groupThe study's sample size calculation below is number of subjects required for each group the makes up the study
- 2-Tailed Sample Size calculation formula for Matched Samples was used in the table below:

(1- β), Power	0.9
α , Level of Significance	0.05
μ_d , mean difference; this is the expected improvement (difference) to treatment assessed by GAIS scores under H_a	1.0
σ_d , Standard Deviation of the difference scores (GAIS range $\div 4$) = [4 \div 4]	1.0
ES, Effect Size $[(\mu_d/\sigma_d)]$	1.0
$Z_{1-\alpha/2}$	1.96
$Z_{1-\beta}$, (for 90%)	0.84
Estimated Sample Size	10.51 \approx 11
Estimated Sample Size + 30% drop out	14.30 \approx 15

Conclusion: The estimated sample size for each cohort group obtained from the primary performance endpoint outcome measure calculation plus 30% drop out provision that will be used for this study is 15.

The study will enroll up to 50 female subjects requesting treatment of surgical scars following breast augmentation or abdominoplasty and up to 25 male and female subjects requesting treatment of surgical scars following face lift surgery.

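### Baseline adjustment is optional, undefined and has no rule on which version is primary; fix one model in advance, on the treated-versus-untreated comparison where adjustment can help

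*Combined protocol and SAP*

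**What the plan says.** Section 10.4.1 (General Approach) makes the main test a paired t-test and/or Wilcoxon signed-ranks test of post-treatment scores against baseline. It then says that, to accommodate imbalances in some baseline GAIS and MSS scores, "covariate adjustment analysis may be performed in SAP to estimate adjusted treatment effects for the primary endpoint analysis". Section 10.4.2, on the primary endpoint, says "Analysis of Covariance (ANCOVA) may also be used where appropriate", and Section 10.4.3 repeats this for the secondary endpoints. No section names a covariate, a model, a size of imbalance that triggers adjustment, or which version decides the endpoint.

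Four other places bear on this:

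- Section 10.1 requires a formal SAP before database lock, but only if the plan is revised.
- Section 10.6.2 leaves the biostatistician unblinded.
- Section 10.4.9 treats multiplicity as not applicable.
- The Protocol Summary says outcomes will be compared with the untreated side, and Section 7.3.2 makes the untreated half of the scar the control and asks for two sets of photographs, "one set for the treated side of the body/face and a second set for the untreated side of the body/face". Yet the hypotheses (10.2), the tests (10.4.1, 10.4.2) and the sample size (10.5) are all post-treatment minus baseline.

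**The concern.** An adjustment that may or may not be made, for an undefined reason, by an unblinded analyst, leaves at least two candidate results for each primary endpoint. If the choice is made after the outcomes are seen, the nominal 5% level no longer holds.

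The wording also leaves open what would be adjusted. Imbalance and adjusted treatment effect are terms for a comparison of two conditions, but the specified test compares one set of scores with its own baseline. Applied to that test, an unspecified ANCOVA can do harm. Applied to the side comparison, a fixed ANCOVA would use baseline data that the trial appears to collect already.

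**Working it through.** **1. The plan's own figure.** Section 10.5 sizes each scar cohort on GAIS at 3 months against baseline: "Expected mean improvement difference is not less than one (1) GAIS score higher than baseline". The mean difference is 1.0, the SD of the differences 1.0, the test two-sided at 5% and the power 90%. This gives n = (1.960 + 1.2816)² = 10.51, rounded up to 11, and 11 × 1.3 = 14.3, rounded up to 15. Both stated figures reproduce. (The 0.84 printed in the table is the 80% value and would give 7.84; that is a separate point.) The calculation involves neither the untreated side nor any adjustment. Evaluable numbers used below: 11 for one cohort, 3 × 11 = 33 pooled, and 52 for full enrolment after 30% loss (75 × 0.7 = 52.5).

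**2. Assumptions.** The documents give no correlation between baseline and follow-up, so r = 0.3, 0.5 and 0.7 are assumed, with equal variances and normal differences.

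**3. Choosing on results.** Let D0 and D1 be the treated-minus-untreated difference at baseline and follow-up. Null trials were simulated and the smaller p-value taken from (a) the paired t-test on D1 − D0 and (b) the intercept of D1 regressed on D0. At n = 11 the error rate is 7.7%, 7.4% and 7.0% for r = 0.3, 0.5 and 0.7. Across n = 11, 33 and 52 it is 6.7% to 7.9%. The regression alone, fixed in advance, gives 4.9% to 5.1% at n = 11.

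**4. The imbalance trigger alone.** The rule simulated was: use (b) if the baseline difference has p below a cut-off (0.05, 0.10, 0.20 or 0.50), otherwise (a). The error rate was between about 3% and 5%, and below 5% in every combination of n, r and cut-off.

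**5. The before-after test as written.** Regressing the change on mean-centred baseline returns the mean change, so the estimate is the same. Its true variance is 2(1 − r)σ²/n, but the model reports (1 − r²)σ²/n, because it ignores the sampling error of the baseline mean. The standard error is too small, and the simulated error rate at n = 11 is 10.1%, 8.2% and 6.7% for r = 0.3, 0.5 and 0.7.

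**6. The side comparison.** Here the expected baseline difference is zero if the side is randomised, so the gain is real. Allowing for estimation of the slope, the variance of (b) relative to (a) is (1 + r)/2 × [1 + 1/(n − 3)].

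| r | (1 + r)/2 | n = 11 (× 1.125) | n = 33 (× 1.033) |
|---|---|---|---|
| 0.3 | 0.65 | 0.731 | 0.672 |
| 0.5 | 0.75 | 0.844 | 0.775 |
| 0.7 | 0.85 | 0.956 | 0.878 |

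Against a follow-up-only side difference the ratio is (1 − r²) × [1 + 1/(n − 3)]. At n = 11 simulation gives 1.03, 0.85 and 0.58, so there is a loss of about 3% at r = 0.3.

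**7. How the side is chosen.** If the two sides differ persistently by d and treatment does nothing, the intercept in (b) has expectation d(1 − r), not zero. At n = 33, for d of 0.2 to 0.5 SD of the side difference, the test in (b) rejects about 7% (d = 0.2, r = 0.7) to 44% (d = 0.5, r = 0.3) of the time. The change-score test stays at 5%.

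**The case against.** The strongest objection is that Section 10 contains no side comparison, so a precision argument addresses an analysis that the plan does not specify. That stands. A reader might infer that the planned primary analysis discards free precision. It does not: step 5 shows that adjustment adds none to a before-after test. Nor is the gain free where it does exist, since in one cohort of 11 it runs from about 27% down to about 4%.

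A reader might also infer that tying adjustment to observed imbalance inflates the error rate. Step 4 shows that it does not. The inflation needs a choice made on results, which the wording permits but does not prescribe. A SAP finalised before database lock could close that gap, but Section 10.1 calls for one only if the plan is revised.

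Two further objections stand and shape the fix. The documents do not confirm that both sides are scored: the schedule of events lists a baseline MSS and reviewer POSAS without naming sides, and the visit text in 7.3.3 and 7.3.4 mentions photographs of the treated area only. And Section 10.6.1, although headed as covering randomisation, gives no rule for the treated side, so an adjusted analysis could itself be biased (step 7).

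**Conclusion.** The point holds in a limited form. Adjustment is optional and linked to undefined imbalances, and no version is named as primary. If the version were chosen on results, the 5% error rate would become about 7% to 8%. That figure was computed for the side comparison and rests on r between 0.3 and 0.7, equal variances and normality. The documents do not show that such a choice is intended.

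The precision benefit belongs only to the treated-versus-untreated comparison promised in the Protocol Summary, which Section 10 must first state. On the same assumptions the variance relative to the change score is about 0.67 to 0.88 at 33 pooled completers and about 0.73 to 0.96 at 11. It does not extend to GAIS, which Section 10.4.2 describes as an improvement rating, so a baseline value has nothing to adjust for. This is a moderate weakness that wording can largely cure, and it should be fixed before the data are seen.

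**What to change.** - Delete the optional adjustment sentence in 10.4.1 and the optional ANCOVA sentences in 10.4.2 and 10.4.3.
- State the treated-versus-untreated comparison in Section 10. For MSS and reviewer POSAS at 3 and 10 months, always fit one model: the treated-minus-untreated follow-up difference on the treated-minus-untreated baseline difference, entered uncentred, with scar type effect-coded (sum-to-zero). Test the intercept, which is then the average effect across the three scar types. With ordinary dummy coding it would be the effect in the reference type only.
- Report the unadjusted change-score side difference as a named sensitivity analysis. Leave GAIS without baseline adjustment.
- Confirm that the blinded reviewer scores both sides at baseline and at follow-up.
- Describe how the treated side is chosen, and state that the adjusted estimate is unbiased only if that choice is random or based on the baseline score.

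The cost is SAP wording, one degree of freedom for the baseline covariate and two for scar type. If the untreated side is not already being photographed and scored at follow-up, that work must be added.

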10.4.2 ANALYSIS OF THE PRIMARY PERFORMANCE ENDPOINT(S)

The following will be considered for the analysis primary performance endpoint:

Summary table for differences of baseline, 3-month and 10-month post treatment General Aesthetic Improvement Scale (GAIS) and Manchester Scar Scale (MSS) scores will be displayed as mean difference, standard deviation and standard error. The General Aesthetic Improvement Scale (GAIS) scores is a 5-point scale improvement assessment chart while Manchester Scar Scale (MSS) is two scales whose scores are combined - an overall VAS and seven scar parameters.

Bar, pie charts or graphs indicating scores will also be used to analyse performance, where applicable.

All statistical tests will be two-sided. The level of statistical significance for effectiveness analyses is 5% ($\alpha = 0.05$) for all tests of differences. Where appropriate, Paired t-test and/or Wilcoxon Signed-Ranks Test for Matched Pairs will be used to compare the evaluations of General Aesthetic Improvement Scale (GAIS) scores and Manchester Scar Scale (MSS) scores at 3 and 10 months against baseline. Analysis of Covariance (ANCOVA) may also be used where appropriate.

The Paired t-test and/or Wilcoxon Signed-Ranks Test for Matched Pairs will enable us to accept or reject the null hypotheses. Rejection of null hypotheses will establish that:

- The two-sided 95% confidence interval for the difference between the means excludes zero.
- The two means are statistically significantly different at the 5% level ($P < 0.05$) two-sided.

Upon rejection of null hypotheses, further statistical test tools such as Confidence Interval and/or t-test will be used to test expected primary performance endpoint; that is alternative hypothesis that $H_a \geq 1$. This will be used to determine if the study meets the primary performance endpoint.

General Aesthetic Improvement Scale (GAIS) scores and Manchester Scar Scale (MSS) scores of all subjects who received at least one treatment of Venus Viva™ system for the treatment of surgical scars following breast augmentation, abdominoplasty or face lift and for whom at least one valid post-baseline GAIS and MSS assessment were obtained will be analysed for the primary endpoint. Multiple imputation method or modelling of available data may be used for missing data as appropriate.

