2.3 POTENTIAL RISKS AND BENEFITS

2.3.1 KNOWN POTENTIAL RISKS

The potential risks for adverse events of the treatment procedure include but are not limited to discomfort or significant pain post-treatment, excessive skin redness (erythema) and/or swelling (edema), in-grown hairs, damage to natural skin texture (crust, blister, burn), change of pigmentation (hyper- and hypo-pigmentation) and scarring. Treatment of hair-bearing areas in male patients may result in some damage to the follicles and subsequent loss of hair. Avoid the beard area and other hair-growing zones if the patient does not wish to experience hair growth reduction.

Further information about residual risks associated with the device and with participation in the clinical investigation are reported in the device User Manual.

Residual risks will be mitigated as follows:

- Selection of Investigator with experience in the therapeutic area of the clinical investigation
- Investigator will undergo training prior to patients' enrollment
- For the first procedure of each site, an experienced person with the use of the device, representing the sponsor, will attend.
- Patients will be rigorously screened prior to their enrollment
- Patients will be rigorously followed over the course of the study

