7.3.4 FINAL STUDY VISIT

Visit 11, Month 12 (\pm 14 days)

Subjects will return to the clinic seven months after the last assessment. Adverse events, vital signs and any changes to concomitant medications will be recorded. Subjects will complete a 5-point Likert satisfaction questionnaire and the POSAS.

Photographs of the treated area will be taken as described in section 7.3.1. The photographs will be sent to the blinded independent reviewer for assessment (GAIS, MSS and POSAS). The termination form will be completed and subjects will be discharged from the clinic and terminated from the study. The PI will

record all reportable events with start dates occurring any time after informed consent is obtained until 7 (for non-serious AEs) or 30 days (for SAEs) after the last day of study participation.

After the study is completed, subjects will be offered treatment on their untreated side (body/face).

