8.2.3 EXPECTEDNESS

Expected (anticipated) adverse reactions are AEs that are common and known to occur for the investigational device being studied. Expected adverse events in this study include discomfort or significant pain post-treatment, excessive skin redness (erythema) and/or swelling (edema), in-grown hairs, damage to natural skin texture (crust, blister, burn), change of pigmentation (hyper- and hypo-pigmentation), scarring. Treatment of hair-bearing areas in males may result in some damage to the follicles and subsequent loss of hair.

An AE or suspected adverse reaction is considered "unexpected" (unanticipated) if it is not known to occur for the investigational device being studied and at the specificity or severity that has been observed (AE not described into the Clinical protocol or User Manual).

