8.3 TIME PERIOD AND FREQUENCY FOR EVENT ASSESSMENT AND FOLLOW-UP

The occurrence of an AE or SAE may come to the attention of study personnel during study visits and interviews of a study participant presenting for medical care, or upon review by a study monitor. All AEs including local and systemic reactions not meeting the criteria for SAEs will be captured on the appropriate CRF. Information to be collected includes event description, time of onset, clinician's assessment of severity, relationship to investigational device and study procedures (assessed only by those with the training and authority to make a diagnosis), and time of resolution/stabilization of the event. All AEs occurring while on study must be documented appropriately regardless of relationship. All AEs will be followed to adequate resolution.

Any medical condition that is present at the time that the participant is screened will be considered as baseline and not reported as an AE. However, if the study participant's condition deteriorates at any time during the study, it will be recorded as an AE.

Changes in the severity of an AE will be documented to allow an assessment of the duration of the event at each level of severity to be performed. AEs characterized as intermittent require documentation of onset and duration of each episode.

The PI will record all adverse events with start dates occurring any time after informed consent is obtained. At each study visit, the investigator will inquire study subjects about the occurrence of AE/SAEs since the last visit. All adverse events need to be followed until resolution or until study end, whichever occurs first.

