10.4.4 SAFETY ANALYSES

The safety analysis will be done by analyzing spontaneous reports of adverse events (AE), subjects' completed 10 cm discomfort/pain VAS and a response questionnaire as well as analysis of immediate and short term response reports by the principal investigator from his/her observation/examination of the treated area. Appropriate Medical Dictionary for Regulatory Activities (MedDRA) code will be used to describe all spontaneously reported or other study related adverse events.

Summaries of spontaneously reported or other study related adverse events will be presented as:

- Number (%) of subjects with any AE,
- Number (%) of subjects with any serious adverse events (SAE),
- Number (%) of subjects permanently withdrawn from treatment due to AE

Summaries of analysis of immediate and short term response reports by the principal investigator examination will be displayed on a bar or pie chart as;

- the overall frequency of subjects with each event (pain during treatment, hemorrhage, burn, erythema, edema, purpura)
- Frequency of subjects with specific severity/intensity for each event using a 5 points scale: 1=none; 2=trace; 3=moderate; 4=marked; 5=severe
- The overall percentage or proportion of subject observed with marked or severe intensity of any event will be calculated and compared to those with none, trace or moderate severity/intensity with the aid of a bar or pie chart.

The following will be considered for the analysis of 10 cm discomfort/pain VAS scores safety data:

Summary table for differences of baseline post-treatment (Visit 2) and Visit 6 post-treatment 10 cm discomfort/pain VAS scores will be displayed as mean difference, standard deviation and standard error. The 10 cm discomfort/pain VAS is a 11-level (0 to 10) ordinal scale tool for assessing pain.

Bar, pie charts or graphs indicating scores, percentages or proportions of subjects with Visit 6 and baseline (Visit 2) post-treatments VAS scores difference that is < 1 and > 1 will be used to analyse subjects' tolerability of this treatment.

All statistical tests will be two-sided. The level of statistical significance for effectiveness analyses is 5% ($\alpha = 0.05$) for all tests of differences. Where appropriate, Paired t-test and/or Wilcoxon Signed-Ranks Test

for Matched Pairs will be used to compare the difference between Visit 2 and Visit 6 post treatment VAS scores.

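### Scarring and pigment change are listed device harms, but the blinded reviewer's scar ratings do not enter the safety analysis and no count of worsened scars is prespecified

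*Combined protocol and SAP*

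**What the plan says.** **Harms.** Section 2.3.1 lists damage to skin texture and "change of pigmentation (hyper- and hypo-pigmentation) and scarring" among the known risks. Section 8.2.3 repeats them as expected adverse events, ending with "change of pigmentation (hyper- and hypo-pigmentation), scarring".

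**Ratings.** The schedule in 7.3.7 has the blinded reviewer score GAIS and MSS at Months 3, 4, 5 and 12, which are 1, 2, 3 and 10 months after the last treatment. Section 7.3.4 states, at the final visit, "The photographs will be sent to the blinded independent reviewer for assessment (GAIS, MSS and POSAS").

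**Analysis of the ratings.** In 10.4.2 the baseline, 3-month and 10-month GAIS and MSS "scores will be displayed as mean difference, standard deviation and standard error". After a test against zero, the expected change of at least 1 is examined, and "This will be used to determine if the study meets the primary performance endpoint". The section adds: "Bar, pie charts or graphs indicating scores will also be used to analyse performance, where applicable". Section 10.4.3 treats the secondary ratings in the same way and permits proportions of improvement and satisfaction scores where applicable.

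**Safety analysis.** Section 10.4.4 opens: "The safety analysis will be done by analyzing spontaneous reports of adverse events (AE"). It adds the pain VAS, a response questionnaire and the investigator's graded examination. GAIS, MSS and POSAS do not appear. Adverse events are summarised as subjects with any event, any serious event, or withdrawal because of an event.

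**Deterioration.** Section 8.3 treats conditions present at screening as baseline, but "if the study participant's condition deteriorates at any time during the study, it will be recorded as an AE".

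**The concern.** The treated tissue is itself a scar, so a scar left worse is a foreseeable form of the listed harm. The blinded ratings are the only masked, structured, long-term record of the scar's appearance, and the plan uses them for performance only.

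The investigator's graded examination cannot take their place. Under 7.3.2 and 10.4.4 it covers six acute signs (pain, hemorrhage, burn, erythema, edema, purpura) up to 30 minutes after treatment. It has no item for scarring or pigment.

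The study's stated objective is safety as well as performance. As planned, the report could show a favourable mean change and an uninformative adverse-event table, and a reader could not tell what share of treated scars the masked reviewer judged to be worse.

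**Working it through.** **1. The plan's own figure.** Inputs from section 10.5: mean GAIS change 1.0, SD of the change 1.0 (range 4 divided by 4), two-sided alpha 0.05, power 90%, dropout 30%.

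- n = ((1.96 + 1.2816) × 1.0 / 1.0)² = 10.51, rounded up to 11.
- 11 × 1.3 = 14.3, rounded up to 15 per cohort.

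Both stated figures reproduce. The printed z of 0.84 would give (1.96 + 0.84)² = 7.84, so it is a labelling slip, separate from this point. The mean of 1 and SD of 1 are therefore the inputs the plan used.

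**2. Share of changes below zero on those inputs.** Section 10.4.1 assumes that paired differences are normal.

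- P(change < 0) = Φ((0 − 1)/1) = Φ(−1) = 0.159.
- A full point worse after rounding: P(change ≤ −0.5) = Φ(−1.5) = 0.067.

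| Number of subjects | Below zero | Full point worse |
|---|---|---|
| 15 (one cohort) | 2.4 | 1.0 |
| 52.5 (75 less 30% dropout) | 8.3 | 3.5 |
| 75 (maximum enrolment) | 11.9 | 5.0 |

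The SD is a range-based convention, so I varied it. With an assumed SD of 1.5, P(change < 0) = Φ(−0.667) = 0.25. With an SD of 2 it is Φ(−0.5) = 0.31. I would not lean on the second figure, because 2 is the largest SD that a direct rating with a range of 4 can have.

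**3. Can a favourable mean coexist with worsening?** Take an assumed cohort of 15 with three subjects at −1, four at +1 and eight at +2.

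- Mean = (−3 + 4 + 16)/15 = 1.13; SD 1.19; SE 1.19/√15 = 0.31.
- Paired t-test p = 0.002; Wilcoxon p = 0.005; 95% CI for the mean 0.48 to 1.79.
- Rated worse: 3/15 = 20%, exact 95% CI 4% to 48%.

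The null hypothesis is rejected and the mean exceeds 1, while one subject in five is worse. Because the interval reaches below 1, the second step in 10.4.2 passes or fails depending on how it is applied, which the section does not settle.

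**4. Where a worsened scar would appear.**

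| Planned output | Shows worsening? | Gives a rate? |
|---|---|---|
| Minimum and maximum (10.4.1) | Most extreme value | No |
| Charts of scores (10.4.2, 10.4.3) | Possibly, where applicable | Not required |
| Individual listings (10.4.10) | Yes | No |
| Adverse-event summary (10.4.4) | Only if recorded as an event | Not by type or relatedness |

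No section defines a worsened scar or plans a count of them.

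**The case against.** A reader might infer that worsened scars are averaged away and vanish from the report. The documents do not support that. Section 10.4.1 requires the median, minimum and maximum in every quantitative table, so a negative extreme would be printed. Charts of a 5-point score would show its distribution. Section 10.4.10 lists every subject by measure and time point.

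The adverse-event route is also real. Section 8.3 makes deterioration an event and requires questioning at each visit, 8.2.2 says that doubtful observations should be reported, and 7.8 covers complaints about appearance. A subject can therefore prompt a report, and it would be wrong to say that capture depends on the unblinded physician alone. Events are also to be MedDRA-coded.

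These points stand, and they narrow the concern. They do not close it. No step turns a reviewer-rated worsening into an adverse event. Section 7.3.4 mentions sending photographs to the reviewer only at the final visit, and non-serious events are recorded for only 7 days after participation ends, so on that reading a rating could come too late to prompt one. Coding events is not the same as planning a table by coded term.

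Two further objections stand in full. The documents do not set out the five GAIS categories, the seven MSS parameters or the direction of MSS, so it is an assumption that either scale registers this harm. And after baseline, the visit descriptions in 7.3.3 and 7.3.4 mention photographs of the treated area only, so untreated-half ratings may not be available as things stand.

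**Conclusion.** The point holds in a limited form. The blinded scar ratings are not linked to safety and no rate of worsening is prespecified, so worsening can be missed in the headline results even though individual cases remain traceable.

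Its size can only be illustrated. On the planning inputs about 16% of changes fall below zero, or about 7% at a full point worse. That rests on a normal curve, on an SD taken from the scale's range rather than from data, on GAIS alone (nothing comparable is given for MSS), and on GAIS having a category for worse. A reader might infer that about 12 of 75 subjects are expected to be harmed. The documents do not support this: 75 is maximum enrolment before dropout, and a value below zero on an assumed curve is not evidence of harm.

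This is a low-cost reporting improvement and does not invalidate the primary analysis. It is worth making because safety is half of the stated objective. The plan already uses a threshold display for safety: 10.4.4 charts the share of subjects whose pain VAS difference is above or below 1.

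**What to change.** In section 10.4.4:

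1. State which GAIS categories count as worse than baseline, and what size and direction of MSS change does. A size threshold for MSS matters because its VAS component would otherwise turn small rating noise into apparent worsening.
2. At 3 and 10 months, and descriptively at 1 and 2 months, report the number and percentage of subjects whose treated half is rated worse by the blinded reviewer, with an exact 95% confidence interval.
3. Show the same count for the untreated half, from the second photograph set required in 7.3.2. Make clear in 7.3.3 and 7.3.4 that both halves are photographed and rated at follow-up.
4. List each worsened subject with whether an adverse event was recorded.

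The cost is one extra table, plus confirmation that the untreated half is photographed and rated after baseline. The safety picture may look less favourable. Some apparent worsening will be rating noise, and the untreated-half count helps the reader judge how much. Precision will be modest: with none worse, the exact 95% upper limit is 22% for 15 subjects and 4.8% for 75.
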